| SAFETY EVALUATIONS | 
The repeat treatment phase evaluated the safety profile of a second injection of Synvisc-One. One hundred and sixty patients were treated during this phase of the study, of which 77 patients received a second injection of Synvisc-One. These patients were followed for 4 weeks and out of 77 patients, only 4 (5.2%) experienced device-related AEs in the injected knee. All such events were mild to moderate and were treated symptomatically. Patients who developed injected knee AEs during the initial phase of the study, and who subsequently received repeat treatment, did not experience injected knee AEs upon repeat exposure to Synvisc-One.
 |
| PLANNED INTERIM ANALYSES | 
There is no interim analysis planned. Serious adverse events will be monitored by the committee on an ongoing basis throughout the study.
 |

| | |
|---|---|
| 
STATISTICS Primary Analysis Endpoint
 | 
The primary endpoint for the study will be analyzed using a responder analysis. The proportion of responders following injection within the 6 months following the baseline injection will be calculated based on Worst Knee Pain scores ≤ 3 on a 0-10 pain scale, which is a threshold consistent with other similar studies (Tubach 2005, Bellamy 2010). The primary endpoint is defined as non-inferiority of the proportion of responders in our study relative to an external criterion for the responder proportion (Bellamy 2010). Bellamy demonstrated in his paper from 2007 (table 3) that a BLISS response at any time during the study was achieved in 70% receiving appropriate care and Hylan G-F 20 and only in 38% of patients receiving appropriate care ($P < 0.0001$). We propose a non-inferiority delta of 20% relative to this external criterion, and thus the primary endpoint will be tested by a test of our sample proportion (p) with null hypothesis $H_0: p < 0.50$ vs. alternative hypothesis $H_1: p \geq 0.50$. This test will be performed using the Wilson-Agresti method for testing a single binomial proportion at a one-sided significance level of 0.025 (i.e. non-inferiority will be satisfied if the 95% Wilson-Agresti (REF BROWN ET AL 2001) interval for the proportion of responders excludes the null rate of 0.50).
 |

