2.1 Primary Objective

There are two primary objectives to this study:

Specific Aim 1: To identify whether injection of 6 mL hylan G-F 20 decreases pain over 26 weeks in young (ages 30 to 50 years) active patients with symptomatic primary osteoarthritis of the knee not treated previously with hylan G-F 20.

Specific Aim 2: Though symptoms can be improved for periods up to 6 months, pain symptoms can recur. The effect of repeated treatments of hylan G-F 20 will be studied.

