13 STATISTICAL METHODS AND CONSIDERATIONS

Prior to the analysis of the final study data, a detailed Statistical Analysis Plan (SAP) will be written describing all analyses that will be performed. The SAP will contain any modifications to the analysis plan described below.

Data Sets Analyzed

The primary endpoint is based on a responder analysis. Response is defined as maintaining a Worst Knee Pain score ≤ 3 on a 0-10 pain scale throughout the 6 months following the baseline injection. Trial success will be based on a non-inferiority test (with 20% non-inferiority threshold) of this response rate in comparison to an external criterion of 70% (Bellamy 2010). Secondary endpoints include determining the duration of response after subsequent injection, determining the effects of treatment on activity levels and quality of life, and describing the three-year time course of each of the study endpoints. The sample size will be $n=150$ subjects followed for up to 3 years after baseline injection. The power to conclude non-inferiority for a true response rate of 65% is better than 92%.

Demographic and Baseline Characteristics

The following demographic variables at screening will be summarized by: race, gender, age, height and weight.

Analysis of Primary Endpoint

The primary endpoint for the study will be analyzed using a responder analysis. The proportion of responders following injection within the 6 months following the baseline injection will be calculated based on Worst Knee Pain scores ≤ 3 on a 0-10 pain scale, which is a threshold consistent with other similar studies (Tubach 2005, Bellamy 2010). The primary endpoint is defined as non-inferiority (with 20% non-inferiority threshold) of the proportion of responders in our study relative to an external criterion of 70% for the responder proportion (Bellamy 2010).

Primary Statistical Analysis: Define the true probability of a subject being a responder as π and the non-inferiority threshold $\delta_{NI} = 0.20$. We require the test of

$$H_0: \pi < 0.70 - \delta_{NI} = 0.50$$

vs. the alternative

$$H_1: \pi \geq 0.70 - \delta_{NI} = 0.50.$$

Non-inferiority will be accepted if the null hypothesis can be rejected with a 2.5% one-sided type I error. To test this hypothesis, we will use the Wilson-Agresti method for a single binomial proportion. Non inferiority will be accepted if the 95% Wilson-Agresti (REF BROWN ET AL 2001) interval for the proportion of responders excludes the null rate of 0.50.

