13.6 Sample Size and Randomization

Bellamy demonstrated in his paper from 2007 (table 3) that a BLISS response at any time during the study was achieved in 70% receiving appropriate care and Hylan G-F 20 and only in 38% of patients receiving appropriate care ($P < 0.0001$). A power calculation using a one-sample comparison of proportion with hypothesized value sample size was performed to determine non-inferiority to the 70% results quoted by Bellamy. Power calculations were measured using STATA's SAMPSI calculator. If we postulate a 20% non-inferiority limit (i.e. that at least 50% of patients receiving G-F 20 will achieve a BLISS response), the sample size required to have 90% power and $\alpha = 0.025$ to show non-inferiority at 50% would be 70. For a 10% non-inferiority limit with 90% power and $\alpha = 0.025$, the required sample size is 274, and for 15% non-inferiority limit with 90% power and $\alpha = 0.025$, it is 124 patients. These numbers do not allow for dropouts, therefore, we intend to recruit 150 subjects to account for dropout.

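### The primary test shows whether the responder rate exceeds 50%, but the plan reports it as non-inferiority to another study's 70%, a claim its 2.5% error does not cover

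*Combined protocol and SAP*

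**What the plan says.** The study is open-label with one arm and no control product (Sections 3.1, 7.1 and 7.3). Aim 1 is "To identify whether injection of 6 mL hylan G-F 20 decreases pain over 26 weeks" (Section 2.1).

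Section 13, Analysis of Primary Endpoint, defines the endpoint as non-inferiority "of the proportion of responders in our study relative to an external criterion of 70% for the responder proportion". The 70% comes from a cited study in which a BLISS response at any time "was achieved in 70% receiving appropriate care and Hylan G-F 20 and only in 38% of patients receiving appropriate care", with P<0.0001 (Synopsis, Primary Analysis Endpoint; same figures in Section 13.6). The Synopsis introduces the margin thus: "We propose a non-inferiority delta of 20% relative to this external criterion". No clinical or statistical reason follows.

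The hypotheses are then written as a true rate below 0.50 against 0.50 or more. The decision rule is: "Non-inferiority will be accepted if the null hypothesis can be rejected with a 2.5% one-sided type I error". In practice this means that the 95% Wilson-Agresti "interval for the proportion of responders excludes the null rate of 0.50". Section 13.6 says that the sample size calculation "was performed to determine non-inferiority to the 70% results", and the Operating Characteristics table is headed as power to conclude non-inferiority.

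**The concern.** A non-inferiority claim compares two quantities, and here only one of them is allowed to vary. The 70% is an observed proportion from a finite sample, yet no sample size, standard error or interval for it is given, and none enters the test or the power table. The error rate of the comparison with the source is therefore larger than that of the test against 0.50.

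What is at stake is the headline sentence of the report. A result just over the line would be described as non-inferior to an earlier hylan result, although the test establishes only that more than half of subjects respond. Readers may also take the result as an answer to Aim 1, which is worded as an effect of the injection.

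**Working it through.** **Inputs.** Null rate 0.50, one-sided 2.5%, Wilson-Agresti interval, n=150 or 120 (Section 13). Source rates 70% and 38%, P<0.0001 (Section 13.6). Source arm size m: not given, so assumed.

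**1. The plan's own test.** The Wilson lower limit exceeds 0.50 when (x/n − 0.50)/√(0.25/n) > 1.95996.
- n=150: x=87 gives 1.9596 (just fails); x=88 gives 2.123 (passes). Smallest success is 88/150 = 58.7%.
- n=120: x=70 gives 1.826; x=71 gives 2.008. Smallest success is 71/120 = 59.2%.

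Both are about 11 points below 70%. The exact binomial error at a true rate of 0.50 is 2.0% (n=150) and 2.7% (n=120), so the test is close to its nominal level for 'rate above 0.50'.

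Exact power at true rates of 0.60 and 0.65 is 61.2% and 92.3% for n=120, matching the stated 61% and 92%. For n=150 it is 66.3% and 95.5%, against the stated 72% and 97%. The stated pair corresponds to a cutoff of 87 (72.1% and 96.9%), which narrowly misses the interval rule. That is a minor side issue.

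**2. What the documents imply about m.** With equal arms and a two-sided two-proportion z-test, the pooled rate is (0.70+0.38)/2 = 0.54 and z = 0.32/√(0.54×0.46×2/m). P<0.0001 needs z of at least 3.891, so m must be at least 74 (z=3.905). I use 74 to 250 per arm. The upper end is an assumption.

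**3. Error of the claim 'within 20 points of the source rate'.** Suppose the true rate here is exactly 20 points below the true source rate, so that the claim is false at its boundary. The true source rate is uncertain around 0.70 with variance 0.70×0.30/m = 0.21/m. The true rate here is then uncertain around 0.50 with the same variance. The chance of declaring success is P(X≥88 of 150) averaged over that distribution:

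| m | error, n=150 |
|---|---|
| 74 | 10.7% |
| 100 | 8.7% |
| 250 | 4.8% |

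A closed-form check uses 1 − Φ(1.96·√(0.25/n)/√(0.25/n + 0.21/m)). For n=150 and m=74 this is 1 − Φ(1.96×0.0408/0.0671) = 11.7%. For m=250 it is 1 − Φ(1.96×0.0408/0.0501) = 5.5%. The normal approximation is slightly higher because the exact cutoff is a little conservative at n=150.

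**4. Where 0.50 sits, as context only.** It is 50 − 38 = 12 points above the source's rate without hylan and 70 − 50 = 20 points below its rate with hylan.

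**5. Are benchmark and endpoint the same quantity?** The source counts a BLISS response at any time. Section 13, Data Sets Analyzed, requires Worst Knee Pain ≤3 'throughout' six months; Analysis of Primary Endpoint says 'within' six months. Under 'throughout', the endpoint is stricter than the source's. Step 3 treats the two as the same quantity.

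**The case against.** The strongest reply is that the plan hides nothing. It writes the null as 0.50, attaches the 2.5% to rejecting that null, calls the 70% an external criterion and tabulates power by true rate. A fixed performance goal is ordinary practice in a single-arm study. All of this stands: neither the test nor its error against 0.50 is at fault. It does not rescue the label, because the endpoint, the decision and the power table are all expressed as non-inferiority.

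A reader might infer three stronger things, none of which the documents support.

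- *That the margin is wrong because it keeps only 12 of 32 points (37.5%) of the source's benefit.* No document sets a retention rule, and 0.50 lies above 38%. The source rates are also any-time responses: under the 'throughout' definition an any-time 70% is a hard target, and 0.50 could be strict rather than lax. What is missing is a justification.
- *That the error could be larger still, with a source arm of about 50.* With 50 per arm, 70% against 38% gives P of about 0.0013, which conflicts with the quoted P<0.0001. An arm that small would need a comparator arm about three times as large.
- *That Aim 1 cannot be addressed at all.* Entry requires pain of 4 to 8 (Section 5.2), so any responder at ≤3 has improved. What is missing is attribution: entry follows a medication washout, and other conservative treatment including oral medication is allowed afterwards (Section 6.1). The lack of a control is openly disclosed and is a limitation of the design, not a contradiction.

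**Conclusion.** The point holds as a mismatch between test and claim. The analysis is an adequate test that the responder rate exceeds 0.50. It does not support non-inferiority to the source's 70% at the stated 2.5%: for that claim the error is about 11% to 5%, assuming equal source arms of 74 to 250 and the same endpoint in both studies. The source arm size is not in the documents, so the range cannot be narrowed, and the difference in response definition means that even this range is indicative. The 20-point margin has no stated reason. Passing 0.50 without a control arm describes response after injection, not response because of it. The planned sample size and the test can stay as they are; what has to change is what the trial may conclude.

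**What to change.** - In the Synopsis (Primary Endpoint, Primary Analysis Endpoint, Rationale for Number of Subjects), Section 13 (Data Sets Analyzed, Analysis of Primary Endpoint, Operating Characteristics) and Section 13.6, replace non-inferiority to 70% with: the responder proportion exceeds a performance goal of 50%. Give the reason for 50% and attach the 2.5% one-sided error to that claim only.
- Report the responder rate and its 95% interval beside both 70% and 38%, stating that the source counts a response at any time.
- Reconcile 'within' and 'throughout' in Section 13 into one response definition. Word the Aim 1 conclusion as an estimate of the responder proportion under that definition, without causal attribution.

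Section 13 says that a detailed SAP, with any modifications, will be written before the final analysis, so it can carry the same wording. The cost is editorial: no extra subjects or data and no change of test. The downside is a more modest claim.

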| 
STATISTICS Secondary Endpoints
 | 
For subsequent injections, duration of response over time and median duration of response will be estimated using survival analysis techniques. Inference for activity levels and quality of life will focus on changes from baseline to 3 months. We will examine the time course for the longitudinal data on pain score, activity level, and quality of life measures across the three years of the study using mixed effects models.
 |
| 
Rationale for Number of Subjects
 | 
Power Calculation
 
Bellamy demonstrated in his paper from 2007 (table 3) that a BLISS response at any time during the study was achieved in 70% receiving appropriate care and Hylan G-F 20 and only in 38% of patients receiving appropriate care ($P < 0.0001$). A power calculation using a one-sample comparison of proportion with hypothesized value sample size was performed to determine non-inferiority to the 70% results quoted by Bellamy. Power calculations were measured using STATA's SAMPSI calculator. If we postulate a 20% non-inferiority limit (i.e. that at least 50% of patients receiving G-F 20 will achieve a BLISS response), the sample size required to have 90% power and
 |

| | |
|------------------------------------|--|
| | 
$\alpha=0.025$ to show non-inferiority at 50% would be 70. For a 10% non-inferiority limit with 90% power and $\alpha=0.025$, the required sample size is 274, and for 15% non-inferiority limit with 90% power and $\alpha=0.025$, it is 124 patients. These numbers do not allow for dropouts, therefore, we intend to recruit 150 subjects to account for dropout.
 
Conservatively assuming a 20% rate of drop-out, the resulting sample size of $n=120$ has better than 90% power (one sided test with $\alpha=0.025$) to show non-inferiority assuming the true responder rate is 65% (i.e. not quite as high as the 70% external reference).
 |
| 
DATA MANAGEMENT PLAN
 | 
Data management and analysis for the study will be performed by the Biostatistics Consulting Unit (BCU) of UCSF’s Clinical and Translational Science Institute (CTSI). Data will be stored on a HIPAA-compliant server. The server room has state-of-the-art environmental controls and security features and is protected by a firewall and anti-virus software.
 |

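### The Wilson-Agresti success rule does not guarantee the stated 2.5% one-sided error: at n=120 the actual error is 2.74%, a small discreteness effect, and the power figures need recomputing for an exact rule

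*Combined protocol and SAP*

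**What the plan says.** The primary test compares the responder proportion with 0.50, which is an external 70% less a margin of 20 points. Section 13 (Data Sets Analyzed) describes it as "a non-inferiority test (with 20% non-inferiority threshold) of this response rate in comparison to an external criterion of 70" percent. The error rate appears twice: the synopsis tests "at a one-sided significance level of 0.025", and Section 13 (Analysis of Primary Endpoint) says "Non-inferiority will be accepted if the null hypothesis can be rejected with a 2.5% one-sided type I error". The method is also named there: "we will use the Wilson-Agresti method for a single binomial proportion", with success if the 95% "interval for the proportion of responders excludes the null rate of 0.50".

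Power is stated in three places:

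- Synopsis, Rationale for Number of Subjects, for 20% dropout and a true rate of 65%: "the resulting sample size of $n=120$ has better than 90% power".
- Section 13, Data Sets Analyzed, directly after the sentence that sets the sample size at 150: "The power to conclude non-inferiority for a true response rate of 65% is better than 92" percent.
- Section 13, Operating Characteristics, Table 1: 61% (n=120) and 72% (n=150) at a true rate of 0.60; 92% and 97% at 0.65.

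Neither the responder cut-off nor the exact error of the rule is given.

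**The concern.** The interval rests on a normal approximation without continuity correction. A responder count moves in whole steps, so the real one-sided error of such a rule lies somewhat above or below its nominal level, depending on n. In a single-arm, open-label study this one rule carries the whole confirmatory claim. At n=120, a result of 71 responders would be declared a success although its exact one-sided p-value is 0.0274. The stated power at n=120 belongs to that same cut-off, so the stated error and the stated power may not both be available at that sample size.

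**Working it through.** **Inputs.** Null rate 0.50, one-sided level 0.025 and the 95% Wilson-Agresti rule (Section 13, Analysis of Primary Endpoint); n=150, and n=120 after 20% dropout (synopsis; Table 1); true rates 0.60 and 0.65 (Table 1).

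**Cut-off.** At a null rate of 0.50 the Wilson lower limit exceeds 0.50 when (X − n/2) / (√n / 2) > 1.96, that is, when X > n/2 + 0.98·√n.

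- n=120: 60 + 10.74 = 70.74, so X ≥ 71. The lower limit is 0.5022 at 71 and 0.4939 at 70.
- n=150: 75 + 12.00 = 87.002, so X ≥ 88. The lower limit is 0.49998 at 87, which just fails, and 0.5067 at 88.

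The Agresti-Coull form gives the same two cut-offs, so the mixed name Wilson-Agresti causes no ambiguity here.

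**Error and power.** For cut-off r, the error is P(X ≥ r | n, 0.50) and the power is P(X ≥ r | n, p), both from the exact binomial.

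| n | Rule | Success from | Error | Power at 0.60 | Power at 0.65 |
|---|---|---|---|---|---|
| 120 | Plan's Table 1 | not given | 2.5% stated | 61% | 92% |
| 120 | Wilson | 71 | 2.74% | 61.2% | 92.3% |
| 120 | Exact binomial | 72 | 1.77% | 54.0% | 89.2% |
| 150 | Plan's Table 1 | not given | 2.5% stated | 72% | 97% |
| 150 | Wilson | 88 | 2.04% | 66.3% | 95.5% |
| 150 | Exact binomial | 88 | 2.04% | 66.3% | 95.5% |

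The plan's n=120 column is reproduced by its own method. At that n, a cut-off of 71 or lower breaks 2.5%, and 72 or higher gives at most 89.2% power at 0.65. No fixed cut-off therefore meets both 2.5% and 90%.

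The plan's n=150 column is not reproduced by its own method. Its 72% and 97% correspond to success from 87 responders (power 72.1% and 96.9%), a rule with an error of 3.00%. The Wilson interval does not exclude 0.50 at that count.

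**Other sample sizes.** Over the 31 values n=120 to 150, the Wilson error ranges from 2.00% (n=126) to 2.99% (n=137), with a mean of 2.49%. It exceeds 2.5% at 14 values. The exact test's power at 0.65 is below 90% only at n=120 (89.2%); it is 91.2% at n=121 and 90.1% at n=122. Just below the range, at n=119, the Wilson rule holds 2.5% (2.16%) and has 90.5% power.

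**The case against.** The strongest defence is that 2.5% is a nominal level. The plan names an approximate interval, cites a source for it, and in the synopsis equates the level with that interval excluding 0.50. It nowhere claims guaranteed error control, and the mean actual error over the range is 2.49%. This stands as a limit on the size of the point, but Section 13 still states the requirement as a 2.5% type I error, and the rule does not ensure it.

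The second defence is that n=120 is only a dropout scenario. Section 11.3 replaces subjects who withdraw from treatment in the first 6 months. The Missing Data paragraph of Section 13 keeps discontinuers in the denominator, as non-responders or by LOCF. Both push the analysed n towards 150, where the Wilson and exact rules coincide. This stands too. The final n is nevertheless unknown, and whether the error holds depends on it.

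A reader might go further in three ways that the documents do not support:

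- That the test is generally anti-conservative. It is not: the error is below 2.5% at 17 of the 31 sample sizes.
- That power above 90% exists only through excess error. This is true at n=120 with a true rate of 65%, by 0.8 points, and at no other n in the range. At a true rate of 70% the exact test at n=120 still has 99.3% power.
- That the sentence claiming better than 92% in Data Sets Analyzed is false. It follows the n=150 statement, and at n=150 both rules give 95.5%.

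**Conclusion.** The point holds and is minor. The prespecified rule does not guarantee 2.5%: the excess is 0.24 points at n=120 and at most 0.49 points between n=120 and 150, and there is none at n=150. At n=120 the stated error and the stated power at 65% cannot both be met, and holding the error costs 92.3 − 89.2 = 3.1 points of power. Neither figure undermines the design. The n=120 powers in Table 1 are correct for the method as named. The larger numerical discrepancy is in the n=150 column, where 72% should be 66% and 97% should be 96% under either rule. These results assume independent subjects, a binomial responder count, and a fixed number analysed.

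**What to change.** In Section 13 and the synopsis, make the primary test an exact one-sided binomial test at 0.025 against 0.50, and report the Wilson interval for display. Section 13 already foresees a detailed SAP before the final analysis, so the change can be made there, before any data are examined. State the cut-offs: 72 of 120 and 88 of 150.

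Then recompute the power figures for that rule:

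- Synopsis, Rationale for Number of Subjects: 89% at n=120 and a true rate of 65%, in place of better than 90%.
- Table 1, n=120: 54% at 0.60 and 89% at 0.65.
- Table 1, n=150: 66% at 0.60 and 96% at 0.65. This correction is needed even if the Wilson rule is kept.
- Data Sets Analyzed: keep the sentence on better than 92%, and say that it refers to n=150.

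The cost is wording plus some power. Within n=120 to 150, and only at the 14 sample sizes where the Wilson rule exceeds 2.5%, power falls by about 2 to 3 points at 65% and 6 to 7 points at 60%. At n=150 the cut-off is the same, so nothing is lost.
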